#### **12.3.4 CA-125 response (GCIg criteria; [Rustin et al 2004](http://ctep.cancer.gov/resources/gcig/respdef_nov2005.doc); [http://ctep.cancer.gov/resources/gcig/respdef\\_nov2005.doc](http://ctep.cancer.gov/resources/gcig/respdef_nov2005.doc))**

Patients will be evaluable for CA-125 response if:

- Diagnosed with ovarian cancer
- a pre-treatment CA-125 level (taken within 2 weeks prior to starting treatment) is at least twice the upper limit of normal, and
- there is no more than a 10% fall in CA-125 between the two pre-treatment samples
- the same assay method is used for each sample from the same patient

A response according to CA-125 will be considered to have occurred if there is at least a 50% reduction in CA-125 levels from the last pre-treatment sample. The response must be confirmed and maintained for at least 28 days. The date when the CA-125 level is first reduced by 50% is the date of the CA-125 response.

## **12.4 Statistical methods and determination of sample size**

### **12.4.1 Statistical evaluation**

[figure not shown]
In order to be able to fully evaluate the effects of the study drugs, the data will be presented individually and summarised using appropriate summary statistics. Details of all listings and summaries to be provided will be included in a comprehensive Statistical Analysis Plan (SAP). This will be prepared and finalised before database lock.

Statistical summaries will be produced by or under the guidance of UK Biostatistics at AstraZeneca Research and Development (R&D) using SAS version 8.1 and, where appropriate, additional validated software.

### **12.4.2 Description of variable in relation to hypotheses**

#### **12.4.2.1 Screening and demographic measurements**

The screening and demographic variables will not address any study objectives per se. They define the population being included in the study and thus contribute to the interpretation of the results of the study.

All demographic data, medical history and details of medications taken before and during the study will be summarised and listed using appropriate summary statistics. Data will be summarised across all patients.

Medications will be coded using the AstraZeneca Drug Dictionary.

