### **Dose Escalation Phase of the continued supply expansion**

The Primary objective is:

- 
- To determine the safety and tolerability profile of higher doses than 200 mg bid, of the melt-extrusion (tablet) formulation (Groups 3 onwards) and to compare the safety and tolerability profile of higher doses than 200 mg bid, of the melt-extrusion (tablet) formulation with 400 mg bid Gelucire® 44/14 (capsule) formulation of AZD2281 (Group 6 and 7).

The Secondary objectives are:

- To determine the single dose and steady state exposures achieved with higher doses of AZD2281 melt-extrusion (tablet) formulation.
- To compare between patients the single dose and steady state exposures of AZD2281 achieved with selected tablet doses and the 400 mg bid capsule dose.
- To describe the efficacy data observed in patients treated with the Gelucire® 44/14 (capsule) formulation and the Melt-extrusion (tablet) formulation.

Exploratory Objectives

- To perform exploratory biomarker analysis and to correlate biomarker data with disease progression/response to therapy from optional archival tumour samples collected from the gBRCA patients enrolled into Group 6 and Group 7.

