**Management of leukopaenia and/or anaemia:** An exception to the management of AZD2281-related toxicity is the occurrence of leukopaenia and/or anaemia. In this case, the AE should be managed as deemed appropriate by the investigator (growth factor, transfusions), without interruption in study drug or change in dose. However, growth factors must be discontinued once the AE has recovered to grade 1 or better. They may be resumed, if necessary, if leukopaenia/anaemia develops again and discontinued once it recovers.

**Management of leukopaenia and/or anaemia (Group 8 and ongoing patients):** An exception to the management of AZD2281-related toxicity is the occurrence of leukopaenia and/or anaemia. In this case, the AE should be managed as deemed appropriate by the investigator (e.g. G-CSF or blood transfusions). However, growth factors must be discontinued once the AE has recovered to grade 1 or better. They may be resumed, if necessary, if leukopaenia/anaemia develops again and discontinued once it recovers. In addition:

- Patients who develop a requirement for repeated blood transfusions within 4-6 weeks should be dose reduced.
- Patients who develop grade 3 anaemia should be dose reduced.

**Management of prolonged haematological toxicities including anaemia, neutropaenia or thrombocytopaenia whilst on study treatment:**

- If any study treatment is interrupted/delayed because of one or more of the following:
- ≥2 week interruption/delay in study treatment due to CTC grade >2 neutropaenia
- ≥2 week interruption/delay in study treatment due to CTC grade >2 thrombocytopaenia
- ≥2 week interruption/delay in study treatment due to CTC grade >2 anaemia and or development of blood transfusion dependence

Weekly blood counts should be performed during the study treatment interruption/delay. If the levels have still not recovered to CTC Grade ≤1 after 4 weeks of dose interruption, the patient should be referred to a haematologist for further investigations. Bone marrow analysis or blood cytogenetic analysis should be considered at this stage according to standard haematological practice. Development of myelodysplastic syndrome should be reported as an SAE and full reports must be provided by the Investigator for documentation on the Patient Safety database.

The dose of AZD2281 must not be adjusted under any other circumstances unless AstraZeneca gives prior agreement. Once the dose of AZD2281 has been reduced under no account should it be re-escalated.

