### **7.2 Screening and demography procedures**

#### **7.2.1 Screening**

The following assessments and procedures should be performed within 28 days prior to first dose of study treatment. For details of the schedule and nature of the assessments, see below.

- Study eligibility (Inclusion/Exclusion criteria) (within 28 days and 7 days prior to study treatment start);
- Signed informed consent (within 28 days prior to study treatment start);
- Demographics (date of birth, gender, and race) (within 28 days prior to study treatment start);
- Serum or urine pregnancy test for women of childbearing potential (within 28 days prior to study treatment start);

- Medical and surgical history (within 28 days prior to study treatment start), including previous cancer and radiotherapy and history of blood transfusions in the previous 6 months;
- Current and concomitant medications including previous cancer therapies (if applicable) (within 28 days and 7 days prior to study treatment start);
- Physical examination, ECOG performance status, vital signs (BP, pulse and body temperature), body weight and height (within 28 days prior to study treatment start);
- ECG (within 7 days prior to study treatment start);
- Haematology, clinical chemistry and urinalysis (within 28 days prior to study treatment start);
- AE recording (within 28 days and 7 days prior to study treatment start);

The following assessments will only be performed for those patients who will be participating in Group 1, 6, 7 and 8 of the Continued supply phase expansion:

- Tumour assessment (CT or MRI scans of chest, abdomen and pelvis for breast cancer and abdomen and pelvis for ovarian cancer with other regions as clinically indicated for the assessment of disease). An historical scan meeting the RECIST criteria as defined in [Appendix F](#) can be used for baseline assessment, but this must be performed no more than 28 days before the first dose of study medication.
- CA-125 (within 28 days prior to study treatment start) in ovarian cancer patients only

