#### **7.2.2.3 Continued Supply Phase and Continued Supply Expansion Phase**

Patients in the Continued Supply Phase and Expansion Phase of the study will have the following assessment performed approximately every 28 days for the first 24 weeks and then at least every 56 days thereafter (28 days = 1 cycle) until treatment discontinuation or study completion (closure of the clinical database). If the patient is still benefiting from taking AZD2281 following study completion, then treatment can be continued. and any new SAEs must be reported to AZ.

The following assessments are included:

- Physical examination including ECOG performance status and vital signs;

- 
- ECG at baseline, Day 1 (if baseline ECG performed greater than 7 day prior to Day 1), end of cycle 1 and cycle 2, when clinically indicated and at final follow-up assessment;
  - Haematology, clinical chemistry and urinalysis;
  - AZD2281 dispensed/returned;
  - AE and concomitant medications (including blood product transfusions and g-CSF support)

For Group 8 patients, physical examination, ECOG performance status, vital signs and ECG assessments should be stopped after Cycle 6 and urinalysis by dipstick should be performed post baseline only if clinically indicated.

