#### **12.4.5 Determination of sample size**

This study is an investigation of the comparative bioavailability of a new Melt-Extrusion (tablet) formulation of AZD2281 compared to the current Gelucire® 44/14 (capsule) formulation. There are no formal statistical analyses of the data planned and no formal sample size calculations have therefore been performed. The size of this study is based upon the desire to gain adequate PK information on the Melt-Extrusion (tablet) formulation whilst exposing as few patients as possible to study procedures.

Within the continued supply expansion phase, tablet doses (commencing at 250 mg bid) with potentially higher average exposure values than the 400 mg capsule dose will be explored and thus, in group 6 and 7 of the continued supply expansion, approximately 15 patients per arm (including at least 10 gBRCA ovarian cancer patients) are required to assess the safety and tolerability of these doses. In addition, as an exploratory measure of clinical activity, to rule out a significant difference between the melt-extrusion (tablet) formulation and the Gelucire® 44/14 (capsule) formulation, change in tumour size at eight weeks will be compared between the tablet dose arm(s) and the 400 mg bid capsule dose arm.

In Group 8, approximately 15 patients per treatment arm will be randomised. In a similar way as per the earlier expansion groups, change in tumour size will be evaluated.

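### Section 12.4.2.1 fixes a pooled summary for baseline data and medications, including transfusions and G-CSF, and no by-arm summary is planned for the randomised groups

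*Protocol*

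**What the plan says.** Section 12.4.2.1 sets the scope, "All demographic data, medical history and details of medications taken before and during the study will be summarised and listed", and then the level of summary, "Data will be summarised across all patients". It adds that these variables help in interpreting the study results.

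Marrow support falls within that scope. Section 7.2.2.3 collects "AE and concomitant medications (including blood product transfusions and g-CSF support", and section 7.2.1 places "history of blood transfusions in the previous 6 months" under medical history. The general rule for leukopaenia and anaemia in section 6.2.4.2 has them "managed as deemed appropriate by the investigator (growth factor, transfusions), without interruption in study drug or change in dose". Group 8 and ongoing patients have a separate paragraph without the no-interruption wording.

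The arms in question carry a safety objective. For Groups 6 and 7 part of the primary objective is "to compare the safety and tolerability profile of higher doses than 200 mg bid" with the 400 mg bid capsule, and section 12.4.5 plans "approximately 15 patients per arm (including at least 10 gBRCA ovarian cancer patients". Table 2 gives the same comparative aim for Group 1. For Group 8 the aim is to determine the safety of four randomised schedules, and section 4.1.2.5 presents this as a randomised comparison.

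**The concern.** The protocol does more than leave the table layout open. It states a level of summary, and for the randomised groups it is the wrong one. A SAP that follows it gives one column mixing single-dose PK patients, escalation patients with any solid tumour, gBRCA breast and ovarian arms, and the Group 8 schedules. Eligibility differs as well: section 5.1 asks for haemoglobin of at least 10.0 g/dL and no transfusion in the preceding 4 weeks in Group 8, but at least 9.0 g/dL in all other groups.

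Two things are at stake. In arms this small, chance imbalance in prognosis or prior treatment is common, and a reader of the tolerability tables needs to see it. Haemoglobin and neutrophil values also respond to transfusion and growth factors. Haematology by treatment is hard to interpret if the support behind it is summarised only over all patients.

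**Working it through.** The protocol gives no figure on this point to reproduce, so the check is first a comparison of sections and then an illustration of size.

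**1. Level of summary by data type**

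| Data | Level stated | Section |
|---|---|---|
| Demographics, medical history, medications | across all patients | 12.4.2.1 |
| Laboratory | by treatment; by dose and formulation | 12.4.2.4, 12.6.2 |
| Pulse and blood pressure | by treatment; by dose and formulation | 12.4.2.5, 12.6.2 |
| Adverse events | for each treatment | 12.6.2 |
| Efficacy | by dose, formulation and schedule | 12.6.3 |

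Section 12.6 adds no table of baseline data or medications. Beside the other rows, the plain reading of the first row is pooled over arms.

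**2. Who would be pooled, read literally**

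The synopsis gives about 20 (PK phase), 26 (Groups 1 and 2), up to 48 (escalation) and up to 135 (Groups 6 to 8): 20 + 26 + 48 + 135 = 229 patients. The parallel randomised arms number 2 (Group 1) + 3 (Group 6) + 2 (Group 7) + 4 (Group 8) = 11. Arm sizes are 20/2 = 10, 45/3 = 15, 30/2 = 15 and 60/4 = 15.

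**3. What a pooled count hides**

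Take two arms of 15 and suppose 6 of 30 patients (20%) received marrow support; the 6 is an assumed figure. The pooled entry is the same for every split below. The p-value is the two-sided Fisher exact test.

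| Split | p |
|---|---|
| 3 vs 3 | 1.00 |
| 2 vs 4 | 0.65 |
| 1 vs 5 | 0.17 |
| 0 vs 6 | 0.017 |

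For the last row, p = 2 × C(15,6)/C(30,6) = 2 × 5005/593775 = 0.017.

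**4. How often chance imbalance occurs**

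Let X₁ and X₂ be independent Binomial(n, p) counts of a baseline factor in two arms. The quantity is P(|X₁ − X₂| ≥ 3), with the prevalence p assumed.

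| n per arm | p | Probability |
|---|---|---|
| 15 | 0.2 | 0.25 |
| 15 | 0.3 | 0.32 |
| 15 | 0.5 | 0.36 |
| 10 | 0.5 | 0.26 |

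A gap of 3 patients is 3/15 = 20 percentage points, or 3/10 = 30 points in Group 1. Check of the last row: at p = 0.5, X₁ − X₂ + 10 is Binomial(20, 0.5), so the probability is 1 − (184756 + 2 × 167960 + 2 × 125970)/1048576 = 1 − 772616/1048576 = 0.26.

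**The case against.** A reader might infer that arm differences cannot be seen at all, or that marrow support is reported only in pooled form. The documents support neither.

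- Section 12.4.2.1 requires listings as well as summaries, and section 12.4.1 promises individual presentation. With 10 to 15 patients per arm, counts can be rebuilt by hand.
- Appendix B gives anaemia needing transfusion as an example of an important medical event. Under section 7.3.3.3 a laboratory deterioration that meets a seriousness criterion is reported as an adverse event, so transfused anaemia should usually appear in the by-treatment adverse event tables. Section 7.3.3.1 records other treatment given for each event, and section 12.2.1 allows events leading to significant additional treatment to be reported as other significant adverse events.
- Section 12.6.2 includes CTCAE laboratory shift tables, so the haematology display is more than means. Section 6.3.2 bars prophylactic G-CSF, so support will generally follow a recorded low value.
- The no-interruption wording does not cover Group 8 or ongoing patients, whose paragraph adds dose-reduction rules. It cannot be applied alike to all the randomised groups.

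These points stand, and they limit the concern. They do not remove it: asymptomatic cytopenia managed with growth factors while dosing continues need not become an adverse event, and none of these routes gives baseline balance.

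Two further objections carry some weight. The section may be PK-phase text carried forward: section 12.4.2.2 beside it calls safety a secondary objective, which fits only that phase, and pooled baseline data are normal in a crossover. That would explain the sentence, but nothing in it limits its scope, and section 12.4.2.7 on the expansion phase is silent on baseline data and medications. Section 12.4.1 also leaves the detail of summaries to the SAP. A SAP could add by-arm tables, but it would have to depart from the stated rule to do so.

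A by-arm table would display a chance imbalance; in arms of 15 it would not by itself separate it from a drug effect.

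**Conclusion.** The point holds in limited form. The protocol fixes a pooled summary for baseline data and medications, including transfusions and G-CSF, and plans no by-arm summary of them. This sits badly with randomised groups whose main purpose is to compare safety (Groups 1, 6 and 7) or to assess it across schedules (Group 8). The planned summaries would not show baseline balance or arm differences in marrow support. These could be rebuilt only from listings, and seen in part through adverse event and shift tables.

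The conclusion rests on reading the pooled rule at face value across all phases. The prevalences and the count of 6 in 30 are illustrations, not protocol figures. Stratification by tumour type in Groups 1, 6 and 7 controls one factor only. No formal safety comparison is planned, so no test result is affected; what suffers is the interpretation of descriptive tables. This is a cheap improvement, not a fault that threatens the study.

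**What to change.** Replace the sentence in section 12.4.2.1 with: *Data will be summarised by group and randomised arm (by dose for the escalation groups), with a total column.* The crossover parts can stay pooled over sequence within cohort or group, since each patient receives both formulations.

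Add a by-arm count of patients receiving blood product transfusion and of patients receiving growth factor support, placed so that it is read beside the haematology tables.

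Splits by tumour type and a table of anti-emetic use are optional; with at least 10 ovarian patients in arms of about 15, at most about 15 − 10 = 5 breast patients per arm would remain in Groups 6 and 7.

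The cost is a few more tables. The data are already collected under sections 6.3.2, 7.2.1 and 7.2.2.3, and no patient procedure changes.

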#### **12.4.2.2 Safety measurements**

The safety data will address the secondary objective to assure the safety of all patients by assessment of pulse, BP, ECG, laboratory data and AEs.

#### **12.4.2.3 Adverse event data**

AE variables are collected as a free text description of the AE and coded using the Medical Dictionary for Regulatory Activities (MedDRA). They will be assessed at the Preferred Term and System Organ Class levels. Other information used in the assessments will be the start and stop date of the AE (if available), maximum NCI-CTCAE grade, whether the event was serious or not and whether the AE was thought, in the opinion of the Investigator, to be associated with the study drug. The definitions of these categories are given in Section 7.4. All AE data will be listed for all patients. Separate listings of all SAEs, deaths, discontinuations or other significant AEs will be presented.

#### **12.4.2.4 Laboratory safety measurements**

All laboratory safety data, incorporating haematology, clinical chemistry and urinalysis data will be listed, with deviations from the range explicitly noted. Numerical laboratory data will be summarised by treatment using standard summary statistics.

#### **12.4.2.5 Pulse and blood pressure**

Absolute pulse and BP data will be listed and summarised using standard summary statistics by treatment.

[figure not shown]
#### **12.4.2.6 Other safety data**

Physical examination details and ECG data will be listed.

#### **12.4.2.7 Continued Supply Expansion Phase**

The primary objective of the Continued Supply Expansion Phase is to assess the multiple dose safety profile of the Melt-extrusion (tablet) formulation in a comparative setting. In terms of safety data, no formal statistical comparisons of data will be performed. Instead, data will be listed and summarised descriptively by formulation (tablet or capsule). Steady state pharmacokinetic and efficacy data will also be collected and summarised by formulation (tablet or capsule).

The secondary objectives of the Continued Supply Expansion Phase (Group 2) is to enable a direct within-patient comparison of the steady state PK of the capsule and the Melt-extrusion (tablet) formulation.

In addition, steady state PK will be assessed in the Group 1 population to determine multiple dose pharmacokinetic parameters for the melt extrusion (tablet) formulation and the Gelucire® 44/14 (capsule) formulation in man. Plasma concentration data and PK parameters will be listed and summarised descriptively using the appropriate standard summary statistics. In terms of efficacy data, summaries and waterfall plots of percentage change from baseline in sum of target lesions will be presented, and this data will also be analysed by analysis of covariance fitting baseline sum of target lesions as a continuous covariate and treatment group as a factor. Summary statistics will be presented for best overall response according to RECIST. PFS will be summarised using Kaplan-Meier estimates over time and will be displayed graphically.

[figure not shown]
### **Dose escalation phase within the continued supply expansion**

The number of patients taking part in this part of the study will be approximately 185.

The primary objective of the dose escalation phase of the continued supply expansion is to determine the safety and tolerability profile of higher doses than 200 mg bid, of the melt-extrusion (tablet) formulation in groups of a minimum of 6 patients – (Groups 3 onwards) and to compare the safety and tolerability profile of higher doses than 200 mg bid, of the melt-extrusion (tablet) formulation with 400 mg bid Gelucire® 44/14 (capsule) formulation of AZD2281 in approximately 45 gBRCA ovarian and breast cancer patients (Group 6) and in 30 gBRCA ovarian and breast cancer patients (Group 7). The primary objective in the randomised tablet formulation continued supply expansion phase (Group 8) is to determine the safety and tolerability profile of selected tablet dose schedules of the melt-extrusion (tablet) formulation. No formal statistical comparisons of safety data will be performed. Instead, data will be listed and summarised descriptively by dose.

The secondary objectives of the dose escalation within the continued supply expansion will involve:

- All patients from Groups 3 onwards contributing to an assessment of the single dose and steady state exposures achieved with higher doses than 200 mg bid of AZD2281 melt-extrusion (tablet) formulation and all patients from Group 6 and 7 contributing to a comparison between patients of single dose and steady state exposures of AZD2281 achieved with selected tablet doses and the 400 mg bid capsule dose. Plasma concentration data and PK parameters will be listed and summarised descriptively using the appropriate standard summary statistics.
- A preliminary assessment of the effect of food by comparison of the Day 8 and Day 1 Cmax and AUC0-24 data from patients in the 400 mg od cohort of Group 8.
- To describe the efficacy data observed in patients treated with the Gelucire® 44/14 (capsule) and the Melt-extrusion (tablet) formulations. Summaries and waterfall plots of percentage change from baseline in sum of target lesions will be presented, and this data will also be analysed by analysis of covariance fitting baseline sum of target lesions as a continuous covariate and treatment group as a factor. Summary

statistics will be presented for best overall response according to RECIST. PFS will be summarised using Kaplan-Meier estimates over time and will be displayed graphically. Analyses will be performed in the overall population and in the gBRCA ovarian cancer subgroup.

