### **2.1.6 Human pharmacokinetic summary**

Following administration of single oral doses of AZD2281 (Gelucire® 44/14 [capsule] formulation) to cancer patients at doses of 10 to 600 mg, absorption is relatively rapid with maximum plasma concentrations achieved between 1 and 3 hours after dosing in the majority of patients. Following the peak, the plasma concentrations decline bi-phasically with a terminal half-life (based on sampling to 24 hours after dosing) of between 5 and 7 hours. The exposures achieved increase proportionally with dose at doses up to 100 mg but increase less than dose proportionally thereafter. The mean volume of distribution and plasma clearance are approximately 40 L and 4.55 L/h.

Following daily administration of AZD2281 on a once or twice daily basis, the pharmacokinetics (PK) showed no marked time dependency with steady state exposure being, respectively, approximately 20 and 50% higher than that following a single dose.

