- 400 mg bid capsule or highest bid tablet dose deemed tolerable by the SRC following completion of the dose escalation phase

Group 8 patients - to further investigate the safety profile and pharmacokinetics of AZD2281 melt-intrusion (tablet) formulation, approximately 60 patients with gBRCA ovarian cancer will be randomised 1:1:1:1 to one of the dosing schedules detailed below:

- 200mg tds tablet continuous dosing

- 
- 250mg tds tablet 2 weeks on study drug, 1 week off study drug
  - 400mg bid tablet 1 week on study drug, 1 week off study drug
  - 400mg od tablet continuous dosing

Patients will continue with their assigned AZD2281 treatment as long as they remain free from intolerable toxicity and, in the Investigator's opinion, are receiving some clinical benefit from treatment with AZD2281 and do not meet any other discontinuation criteria. Following the commencement of continuous treatment of either formulation, study safety assessments will be performed monthly for the first 6 months and then every 8 weeks until treatment discontinuation or study completion (closure of the clinical database - see Section 10.5). If a patient remains on study treatment following the completion of the study (closure of the clinical database), SAEs will continue to be collected until treatment discontinuation.

If the data demonstrate that one treatment arm is significantly more efficacious, then patients who are ongoing on treatment in the less efficacious arm may be permitted to switch to the more efficacious treatment arm following agreement of the investigator and the AZ study physician.

Doses of AZD2281 should be taken at the same times each day, daily (OD) doses should be taken in the morning unless otherwise instructed, twice daily (BD) doses should be taken approximately 12 hours apart and three times (TDS) daily doses taken approximately 8 hours apart. All doses should be taken with approximately 240 mL of water.

Patients will be instructed to take their doses of AZD2281 at least 2 hours after the last time they ate, and the patient should then refrain from eating for a further 2 hours due to the potential effect of food on absorption. For Group 8 patients (excluding Group 8 od schedule patients), and for all other patients (PK phase cohorts 1 and 2, and Groups 1-7) continuing to receive tablet doses following approval of Amendment 4, AZD2281 can be taken with a light meal and the time restrictions on eating will not apply.

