For Group 8 od schedule patients an informal assessment of the effect of food on the PK of AZD2281 will be made. On Day 1 these patients must take their dose of AZD2281 at least 2 hours after the last time they ate, and then refrain from eating for a further 2 hours. On Day 8 patients must take their dose of AZD2281 within 30 minutes of eating breakfast. On all other days doses can be taken with a light meal, and no time restrictions are required.

All ongoing patients taking capsule doses of AZD2281 must continue to take their doses of AZD2281 at least 2 hours after the last time they ate, and then refrain from eating for a further 2 hours due to the potential effect of food on absorption of the capsule formulation.

The capsules/tablets should be swallowed whole and not chewed, crushed, dissolved or divided.

If vomiting occurs shortly after the AZD2281 capsules/tablets are swallowed, the dose should only be replaced if all of the intact capsules/tablets can be seen and counted. Should any patient enrolled on the study miss a scheduled dose for whatever reason (eg, as a result of forgetting to take the capsules/tablets or vomiting), the patient will be allowed to take the scheduled dose up to a maximum of 2 hours after that scheduled dose time. If greater than 2 hours after the scheduled dose time, the missed dose is not to be taken and the patient should take their allotted dose at the next scheduled time.

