For the patients in Group 1 of the Continued supply phase, non-linear mixed effects modelling will be used for the evaluation of the AZD2281 steady state plasma concentration-time data to determine the maximum steady state drug concentration in the plasma during the dosing interval ( $C_{ss,max}$ ), the minimum steady state drug concentration in plasma ( $C_{ss,min}$ ) and the area under the plasma concentration-time curve during the dosing interval at steady state (AUCss). For those patients in Group 2, non-compartmental methods will be used for the evaluation of the steady state plasma concentration-time data to determine  $C_{ss,max}$ ,  $C_{ss,min}$  and AUCss for both the Melt Extrusion (tablet) formulation and the Gelucire® 44/14 (capsule) formulation. For the patients in Groups 3 to 8 non compartmental methods will be used to determine single dose  $C_{max}$ ,  $C_{min}$  and  $AUC_{0-8}/AUC_{0-12} / AUC_{0-24}$  and non-linear mixed effects modelling will be used to determine steady state  $C_{ss,max}$ ,  $C_{ss,min}$ , and AUCss.

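### The Group 8 food-effect ratio sets a fed Day 8, after seven daily doses, against a fasted first dose on Day 1, so its no-effect value is about 1.04 to 1.20 and not 1

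*Protocol*

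**What the plan says.** The food effect on tablet exposure is a secondary objective of Group 8. The synopsis fixes the outcome as the Day 8 to Day 1 ratios of Cmax and AUC0-24, and section 12.4.2.7 describes "A preliminary assessment of the effect of food by comparison of the Day 8 and Day 1" values in the 400 mg once-daily cohort.

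Section 6.2.3.2 sets the conditions for that arm:

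- Schedule: "400mg od tablet continuous dosing".
- Day 1: "On Day 1 these patients must take their dose of AZD2281 at least 2 hours after the last time they ate", with no food for two hours afterwards.
- Day 8: "On Day 8 patients must take their dose of AZD2281 within 30 minutes of eating breakfast".
- Otherwise: "On all other days doses can be taken with a light meal, and no time restrictions are required".

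Table 7 (footnote o) and section 7.2.2.3 give Days 1 and 8 in this arm the same 13-point sampling to 24 h. Day 57 is sampled sparsely, in time windows.

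Section 2.1.6, which reports capsule data, describes once- and twice-daily dosing "with steady state exposure being, respectively, approximately 20 and 50% higher than that following a single dose".

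**The concern.** Two things differ between the numerator and the denominator of the ratio. Day 8 is fed and Day 1 is fasted; Day 8 is at steady state and Day 1 is a first dose. Both change in every patient and in the same direction, so the data cannot separate them. Any other change over the first week (a period effect) goes into the same number.

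No other profile in the arm helps. There is no fasted steady-state profile and no fed first-dose profile, and on Day 57 sampling is sparse and a light meal is allowed. The protocol neither corrects for accumulation nor names it as a limitation.

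At stake is the reading of a named secondary outcome. A reader will naturally take 1 as the value for no food effect. With accumulation present that value is above 1, so a food-related fall can be hidden and a rise exaggerated.

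**Working it through.** **Model.** Expected Day 8 : Day 1 ratio = F × A × P, where F is the food effect, A the accumulation from single dose to steady state, and P any period effect. Below, P = 1.

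**Is Day 8 at steady state?** Day 1 to Day 8 is 168 h. At the longest stated half-life, 168 / 7 = 24 half-lives, so yes.

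**A from the protocol's reported figure.** Section 2.1.6 gives about 20% for once-daily dosing, so A ≈ 1.20. This is an observed result and cannot be reproduced from inputs, but it can be cross-checked.

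**A from the stated half-life.** Under linear superposition with a 24 h interval, A = 1 / (1 − exp(−24 ln 2 / t½)).

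- t½ = 5 h: 1 / (1 − 0.036) = 1.037
- t½ = 6.09 h (ln 2 × 40 L / 4.55 L/h, from the volume and clearance in section 2.1.6): 1 / (1 − 0.065) = 1.070
- t½ = 7 h: 1 / (1 − 0.093) = 1.102

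A one-compartment oral model with half-life 5 or 7 h and an assumed absorption rate of 0.5 to 4 per h gives 1.04 to 1.13. Cmax and AUC0-24 are inflated by nearly the same factor, so both outcomes are affected.

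**Do the two sources agree?** Not exactly. A = 1.20 needs exp(−24 ln 2 / t½) = 1 − 1/1.2 = 1/6, so t½ = 24 × ln 2 / ln 6 = 9.3 h, longer than the stated 5 to 7 h. Section 2.1.6 describes a bi-phasic decline sampled to 24 h, which may understate the terminal half-life. Neither source is tablet data. The supportable range for the no-effect ratio is therefore 1.04 to 1.20, above 1 throughout.

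**What the ratio would show.**

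| A | Ratio if F = 1 | True F that reads as 1.00 (1/A) | Ratio if F = 1.25 |
|---|---|---|---|
| 1.04 | 1.04 | 0.96 | 1.30 |
| 1.07 | 1.07 | 0.93 | 1.34 |
| 1.10 | 1.10 | 0.91 | 1.38 |
| 1.20 | 1.20 | 0.83 | 1.50 |

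A food-related fall of 4% to 17% would thus read as no effect, depending on A.

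**The case against.** The best defence is that the protocol claims little. It calls the assessment preliminary and informal, it rests on one arm of about 15 patients, and section 2.3 says a further food-interaction study of the tablet is to be done. This stands as a reason for a lower severity. It does not remove the defect: those labels excuse imprecision, whereas this is a bias that more patients would not reduce.

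Several stronger readings are tempting, but the documents do not support them:

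- *That the ratio will be 1.20 if food does nothing.* This is a capsule figure and the top of the range; the stated half-life gives 1.04 to 1.10.
- *That a false-positive rate can be attached to the comparison.* The protocol plans no confidence interval, test or threshold for it. The 90% interval in section 12.4.4.1 belongs to the PK-phase cohorts.
- *That the two days are derived by different methods.* For Groups 3 to 8, section 12.1.1 says "non-linear mixed effects modelling will be used to determine steady state" parameters, and Day 8 is at steady state. But the food outcome is named Cmax and AUC0-24 on both days, the labels that section gives to non-compartmental analysis, and Day 8 has full sampling. This is an ambiguity to settle and no more.
- *That single-dose exposure across the four schedules is confounded with food.* The other three schedules do have no fasting rule on Day 1, but Group 8 PK is only listed and summarised, and no cross-schedule test of exposure is planned.
- *That the result decides whether tablets may be taken with food.* No section links the two. For the other Group 8 schedules and continuing tablet patients, section 6.2.3.2 already says "AZD2281 can be taken with a light meal and the time restrictions on eating will not apply".

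**Conclusion.** The point holds. As designed, the Day 8 to Day 1 ratio in the once-daily arm estimates food effect times accumulation and any period effect. The direction of the accumulation bias is clear: with no food effect and no period effect the ratio lies above 1. Its size is uncertain, at about 1.04 to 1.10 from the stated half-life and up to about 1.20 on the reported once-daily figure.

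This rests on carrying capsule kinetics over to the tablet, for which the protocol gives no once-daily accumulation figure, and on food and accumulation acting multiplicatively. Section 2.1.6 speaks of exposure without separating Cmax from AUC. Severity is moderate to minor, because the assessment is preliminary and a further study is announced.

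**What to change.** **For patients not yet dosed.** Randomise the order of the two PK days within the once-daily arm: about half fasted on Day 1 and fed on Day 8, the rest the reverse, with the prandial conditions left as the protocol defines them. Analyse log Cmax and log AUC0-24 with patient, day and food as factors. Accumulation and period then fall into the day effect, and the no-effect value of the food ratio returns to 1.

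Precision is essentially unchanged. With within-patient SD s on the log scale, the paired ratio has SE = s × √(2/15) = 0.365s. A 7/8 split gives s × √(½ × (1/7 + 1/8)) = 0.366s. Visits and samples stay the same; the change needs amendment wording and a short randomisation list. The cost is that about half the arm no longer gives a fasted single-dose profile.

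**For patients already dosed.** Divide Day 8 AUC0-24 by Day 1 AUC0-infinity, since the two are equal without a food effect under linear, time-independent kinetics. This is approximate. Section 2.1.6 supports time-independence but reports less than dose-proportional capsule exposure above 100 mg. If accumulation is really 1.20 while the half-life is 5 to 7 h, a residual of 1.20/1.102 = 1.09 to 1.20/1.037 = 1.16 remains. It does nothing for Cmax, so report the Cmax ratio as food and accumulation combined and read it against 1.04 to 1.20.

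**In either case.** State in section 12.1.1 that the Day 1 and Day 8 values used for the food comparison both come from non-compartmental analysis, and name accumulation as a limitation wherever the fixed-order ratio is reported.
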